1.4 Masking

This study is assessor-masked.

2 Analysis Sets

[figure not shown]
2.1 Safety Analysis Set

Safety analyses will be conducted using the safety analysis set on a treatment-emergent basis. As such, the safety analysis set will include all subjects/eyes exposed to any study treatment evaluated in this study. For treatment-emergent safety analyses, subjects/eyes will be categorized under the actual study treatment exposed.

Adverse events occurring from the time of informed consent but prior to first exposure to study treatment will be summarized in subject listings.

2.2 Full Analysis Set

The full analysis set (FAS) is the set of all randomized subjects who are exposed to any study treatment evaluated in this study.

3 Subject Characteristics and Study Conduct Summaries

The following tables will be presented:

Subject Disposition

Document ID: V-CLN-0002145

Page 8 of 23 Approved Date: 09 Nov 2020

- Analysis Sets
- **Subject Accounting**
- Demographics Characteristics
- Baseline Characteristics

Demographic characteristics and subject accounting tables will be summarized by	y study
treatment group and overall	Baseline
characteristics will be summarized by study treatment group and over all	

In addition, the following subject listings will be provided:

- Listing of Subjects Excluded from Protocol Defined Analysis Sets
- Listing of Treatment Assignment by Investigator
- Listing of Subjects Discontinued from Study

4 **Effectiveness Analysis Strategy**

This study defines 1 primary	
endpoint.	FAS as the primary analysis set.

Continuous variables will be summarized using the number of observations, mean, standard deviation, median, minimum and maximum, as well as confidence intervals/limits as applicable. Categorical variables will be summarized with counts and percentages from each category. In addition, change from baseline data will be summarized, for selected endpoints. For each subject and for each eye (if applicable) with available data, change from baseline will be computed at a particular visit, Visit *i*, as follows:

change from baseline_i = (post-baseline value_i – baseline value),

where

post-baseline value = data at Visit i, i = applicable post-baseline visit

baseline value = data at Visit 1

All data obtained in evaluable subjects/eyes will be included in the analysis. No imputation
for missing values will be carried out
4.1 Effectiveness Endpoints
Primary Endpoint
The primary endpoint is change from baseline in MGS, which is derived from MGS, calculated separately for each eye (total from 15 glands), where baseline is defined as Visit 1

[figure not shown]
4.2 Effectiveness Hypotheses

[figure not shown]
Primary Effectiveness

The null and alternative hypotheses for the primary analysis are formulated in terms of the predefined margin of 5 for noninferiority:

$$\begin{split} H_0: \; & \; \mu_{(iLux)} - \mu_{(Lipiflow)} \leq \text{-}5 \\ & \; H_a: \; & \; \mu_{(iLux)} - \mu_{(Lipiflow)} > \text{-}5 \end{split}$$

where $\mu_{(iLux)}$ and $\mu_{(Lipiflow)}$ denote the mean change from baseline in MGS for iLux and LipiFlow, respectively.

[figure not shown]

[figure not shown]

[figure not shown]
4.3 Statistical Methods for Effectiveness Analyses

4.3.1 Primary Effectiveness Analyses

A mixed effects repeated measures model will be utilized to test these hypotheses. The model will include terms for treatment, visit, treatment by visit interaction, and baseline MGS. Within-subject correlation due to eye will also be accounted for in the model. Site and site by treatment interaction terms will be included as random effects to account for potential effect of sites on treatment difference. Treatment difference (iLux minus LipiFlow) and the corresponding one-sided 95% lower confidence limit (LCL) will be computed. Noninferiority in change from baseline in MGS will be declared if the LCL is greater than -5.

Status: Approved, Version: 3.0

Approved Date: 09 Nov 2020

5 Safety Analysis Strategy

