Short Title:

Statistical Analysis Plan DEG723-P001 / NCT03956225

Full Title:

Statistical Analysis Plan DEG723-P001

Protocol Title: Comparison between iLux and LipiFlow in the treatment of

Meibomian Gland Dysfunction (MGD): A 12-month,

Multicenter study

Approvals: See last page for electronic approvals

Job Notes:

This is the second revision (Version 3.0) of the Statistical Analysis Plan for this study. This version of the Statistical Analysis Plan is based on Version 3.0 of the study protocol.

V-CLN-0002145

Status: Approved, Version: 3.0 Page 2 of 23 Approved Date: 09 Nov 2020

Executive Summary:

Key Objectives:

Document ID:

The primary objective is to demonstrate noninferiority in change from baseline in Meibomian Gland Score (MGS) with iLux Device (iLux) when compared to LipiFlow Thermal Pulsation System (LipiFlow) at the 12-Month Follow-up visit.

Decision Criteria for Study Success:

Success of this study will be based on demonstration of noninferiority in change from baseline in MGS at 12 months post single treatment with iLux when compared to LipiFlow, using a margin of 5.

Table of Contents

Statistic	ical Analysis Plan DEG723-P001	1
Table of	of Contents	3
List of 7	Tables	4
List of I	Figures	4
1	Study Objectives and Design	5
1.1	Study Objectives	
1.2	Study Description	
1.3	Randomization	6
1.4	Masking	6
2	Analysis Sets	7
2.1	Safety Analysis Set	7
2.2	Full Analysis Set.	7
3	Subject Characteristics and Study Conduct Summaries	
4	Effectiveness Analysis Strategy	8
4.1	Effectiveness Endpoints	9
4.2	Effectiveness Hypotheses	10
4.3	Statistical Methods for Effectiveness Analyses	11
4.3.1	Primary Effectiveness Analyses	11
5	Safety Analysis Strategy	16
5.1	Safety Endpoints	16
5.2	Safety Hypotheses	16
5.3	Statistical Methods for Safety Analyses	16
5.3.1	Adverse Events	16

Page 4 of 23

[figure not shown]
5.3.2	Biomicroscopy Findings	17
5.3.3	Device Deficiencies	17
6	Analysis Strategy for Other Endpoints	17
7	Sample Size and Power Calculations	17
8	Other Reporting Considerations and Analysis Strategies	18
9	References	19
10	Revision History	19
11	Appendix	22
T 11 1 1	List of Tables	_
Table 1-1	Study Description Summary	5
Table 8-1	Analysis Windows	18
Table 11-	1 Overview of Study Plan	22
	List of Figures	
Figure 1-	-1 Study Design	6

1 Study Objectives and Design

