1.2 Study Description

Key components of the study are summarized in Table 1-1.

Table 1-1 Study Description Summary

Study Design	Prospective, randomized, parallel group, assessor-masked,				
	controlled				
Study Population	The study population will consist of adult male and female				
	subjects \geq 18 years old at the time of informed consent. Subjects				
	must have signs and symptoms of EDE in both eyes.				
	Target to complete: 188				
	Planned to enroll: ~278				
Number of Sites	~15				
	(US)				
Test Product	iLux Device (iLux)				
Control Product	LipiFlow Thermal Pulsation System (LipiFlow)				
Duration of Treatment	Approximately 12 months				
Visits	Visit 1: Screening/Baseline				

[figure not shown]
Visit 2: Treatment [1-7 days from Visit 1]*
Visit 3: 2-Week Follow-up [14 days (± 3 days) from Visit 2]
Visit 4: 1-Month Follow-up [30 days (± 3 days) from Visit 2]
Visit 5: 3-Month Follow-up [90 days (± 7 days) from Visit 2]
Visit 6: 6-Month Follow-up [180 days (± 14 days) from Visit 2]
Visit 7: 9-Month Follow-up [270 days (± 25 days) from Visit 2]
Visit 8: 12-Month Follow-up [365 days (± 45 days) from Visit 2]
*Randomization will occur at Visit 2

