5.3.3 Device Deficiencies

The following tables and supportive listings will be provided:

- Frequency of Treatment-Emergent Device Deficiencies
- Listing of Treatment-Emergent Device Deficiencies
- Listing of Device Deficiencies Prior To Treatment Exposure

6 Analysis Strategy for Other Endpoints

Not applicable

7 Sample Size and Power Calculations

The sample size calculation for the primary endpoin is based on a prior clinical study that assessed performance of the LipiFlow and iLux devices.

Primary Effectiveness

To demonstrate noninferiority (margin = 5) in change from baseline in MGS as a one-tailed hypothesis with α =0.05, and using a standard deviation of 11.661, 90% power can be attained with a sample size of 188 (94 per treatment group).

[figure not shown]

[figure not shown]
9 References

Not Applicable

10 Revision History

This is the second revision (Version 3.0) of the Statistical Analysis Plan for this study. This version of the Statistical Analysis Plan is based on Version 3.0 of the study protocol. The purpose of this revision is to clarify specific reporting considerations and analysis strategies.

11 Appendix

Table 11-1 Overview of Study Plan

Visit	Visit 1 Screening / Baseline	Visit 2 Treatment	Visit 3 2-Week Follow-up	Visit 4 1-Month Follow-up	Visit 5 3-Month Follow-up	Visit 6 6-Month Follow-up	Visit 7 9-Month Follow-up	Visit 8 12-Month Follow-up/ Exit	Unscheduled Visit / Early Exit
Day Number	Day 0	1 – 7 days after screening	14 days (post treatment) ± 3 days	30 days (post treatment) ± 3 days	90 days (post treatment) ± 7 days	180 days (post treatment) ± 14 days	270 days (post treatment) ± 25 days	365 days (post treatment) ± 45 days	N/A
Informed Consent	√	-	-	-	-	-	-	-	-
Demographics	✓	-	-	-	-	-	-	-	-
Medical History	✓	-	-	-	-	-	-	-	-
Concomitant Medications	✓	√	√	√	✓	✓	√	✓	√
Inclusion/Exclusion	✓	-	-	-	-	-	-	-	-
		I	•	•			•		I
	•	•	I	I	ı	ı	I	ı	I
		7	I	ı	ı	ı	I	ı	I
		-							I
	-	7	-	-		•	-	•	1

Document ID:

V-CLN-0002145

Status: Approved, Version: 3.0 Approved Date: 09 Nov 2020

Page 23 of 23

Visit	Visit 1 Screening / Baseline	Visit 2 Treatment	Visit 3 2-Week Follow-up	Visit 4 1-Month Follow-up	Visit 5 3-Month Follow-up	Visit 6 6-Month Follow-up	Visit 7 9-Month Follow-up	Visit 8 12-Month Follow-up/ Exit	Unscheduled Visit / Early Exit

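### The primary model uses one baseline-MGS slope for all six follow-up visits; a baseline-by-visit term could make the 12-month test slightly more precise at very small cost

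*SAP*

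**What the plan says.** SAP 4.3.1 and Protocol 12.4.1.2 give the same list of fixed effects: "The model will include terms for treatment, visit, treatment by visit interaction, and baseline MGS". Baseline MGS appears once, as a main effect. The visit interaction is written out for treatment and for nothing else. Both documents also account for the correlation between a subject's two eyes, and the SAP adds: "Site and site by treatment interaction terms will be included as random effects to account for potential effect of sites on treatment difference".

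MGS is assessed at six post-treatment visits: 2 weeks and 1, 3, 6, 9 and 12 months. The last is "Visit 8: 12-Month Follow-up [365 days (± 45 days) from Visit 2". The SAP's Executive Summary puts the decision at that visit alone: "Success of this study will be based on demonstration of noninferiority in change from baseline in MGS at 12 months post single treatment".

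SAP Section 7 sizes the trial with a margin of 5 and a "one-tailed hypothesis with α =0.05", and states that "90% power can be attained with a sample size of 188 (94 per treatment group", based on a standard deviation of 11.661. It mentions no gain from baseline adjustment.

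**The concern.** The outcome is change from baseline. If MGS soon after treatment depends little on where the eye started, the slope of change on baseline is near -1. If the effect then fades and each eye returns toward its own starting level, the slope moves toward 0. A single coefficient fits a weighted average of these slopes, which need not equal the 12-month slope.

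Any chance difference in baseline MGS between arms is then corrected at month 12 by somewhat the wrong amount. Over repeated trials this appears as extra variance in the 12-month difference, and so as a wider interval around the one estimate whose lower limit is compared with -5. The model lets treatment vary by visit but holds the baseline slope constant without saying why.

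**Working it through.** **Inputs from the documents.** Margin 5, one-sided alpha 0.05, SD 11.661, 94 per group (SAP Section 7; Protocol 12.8); six visits (SAP 1.2); 236 randomized to yield 188 completers (Protocol Section 8).

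**Assumptions, because the documents are silent.** Baseline SD (SDb) 3, 5 or 7. 11.661 is the unadjusted SD of 12-month change. Correlation over visits is either 0.5 throughout (CS) or 0.7 per 3 months (AR). Slopes move linearly in time from 2 weeks to month 12: mild drift -0.9 to -0.4, strong drift -1.0 to -0.1. Analysis is at subject level, without eye or site effects.

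**Step 1: the plan's own figure.** n = 2 × (1.645 + 1.282)² × 11.661² / 5² = 93.2, so 94 per group. SE = 11.661 × √(2/94) = 1.701. Power = Φ(5/1.701 − 1.645) = 90.2%, or 90.04% by the noncentral t. The stated size is reproduced.

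**Step 2: variance of the 12-month difference.** Let b12 be the 12-month slope and s² = 11.661² − b12² × SDb².

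- By-visit slopes: V = (2s²/94) × (1 + 1/186).
- Common slope: V = 2s²/94 + (2 SDb²/94) × (b_common − b12)² + (2s²/94) × q/186.

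Here b_common is the inverse-covariance-weighted mean of the six slopes, and q is the variance of that weighted mean relative to a single visit. Under CS, each visit has weight 1/6 (0.17) and q = 0.5 + 0.5/6 = 0.583. Under AR, month 12 has weight 0.35 and q = 0.596.

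**Step 3: one case in full (strong drift, SDb 7, CS).** The mean visit time is (0.5 + 1 + 3 + 6 + 9 + 12)/6 = 5.25 months, so b_common = −1 + 0.9 × (5.25 − 0.5)/11.5 = −0.628, which is 0.528 away from −0.1. s² = 135.98 − 0.01 × 49 = 135.49, and 2s²/94 = 2.883.

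- By-visit: 2.883 × 1.00538 = 2.898.
- Common: 2.883 + 1.0426 × 0.279 + 2.883 × 0.583/186 = 3.183.
- Ratio 1.098. Power is Φ(5/√2.898 − 1.645) = 90.18% against Φ(5/√3.183 − 1.645) = 87.65%.

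**Step 4: variance ratio, common over by-visit.**

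| SDb | Mild, CS | Mild, AR | Strong, CS | Strong, AR |
|---|---|---|---|---|
| 3 | 1.004 | 1.002 | 1.016 | 1.011 |
| 5 | 1.014 | 1.010 | 1.049 | 1.035 |
| 7 | 1.031 | 1.022 | 1.098 | 1.071 |

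Simulation on complete data (1,500 trials per scenario) gave 1.003 to 1.023 for mild drift and 1.017 to 1.104 for strong drift.

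**Step 5: another drift pattern.** Set b12 = −0.5, with the first five slopes all lower by 0.3 or 0.5. The variance ratio is 1.000 to 1.022 for a gap of 0.3 and 1.005 to 1.066 for a gap of 0.5. The worst power comparison is 92.34% by-visit against 90.85% common. Every case stays above 90%.

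**Step 6: the cost if slopes are equal.** The ratio is (1 + 0.583/186)/(1 + 1/186) = 0.998, so the by-visit model is 0.2% worse in variance. Simulation gave 0.995 to 0.997, so up to 0.5% worse. Break-even at b12 = −0.5 comes when the common slope is off by √[(1 − q)s²/(186 SDb²)]. For SDb 5 under CS this is √(0.417 × 129.73/4650) = 0.108. For SDb 3 and 7 it is about 0.18 and 0.075.

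**Step 7: dropout.** With 236 randomized and 20% random monotone dropout (planned: 1 − 188/236 = 20.3%), 1,500 runs per case under CS and the Step 5 pattern gave SE ratios of 0.999 (gap 0, SDb 5), 1.009 (gap 0.3, SDb 5) and 1.042 (gap 0.5, SDb 7). The last is 1.042² = 1.086 in variance. Mean error was within 0.04 points for both models.

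**The case against.** The listed model is valid and prespecified, and nothing in the documents shows that the slopes drift. That stands: the loss is possible, not established. If the common slope is off by less than the break-even in Step 6, the simpler model is the more precise one.

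A reader might go further than the documents allow in four ways.

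- **That the slope comes only from the early visits.** It does not. It averages all six visits, and month 12 carries weight 0.17 to 0.35 in the cases above.
- **That the interaction is free.** It costs five parameters and a little precision when slopes are equal.
- **That the 12-month estimate is biased.** Randomization makes baseline imbalance a matter of chance. With 94 per arm its SE is SDb × √(2/94), that is 0.44, 0.73 or 1.02 points for SDb 3, 5 or 7. A slope error of 0.3 therefore moves the estimate by 0.13, 0.22 or 0.31 points per SE of imbalance. This is the same variance effect seen in one trial, not a second harm.
- **That the trial is too small.** The stated size reproduces and takes no credit for baseline adjustment. Power clearly below 90% needs strong drift together with a wide baseline spread.

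Two more objections limit the precision of the figures. The calculation omits eyes and the SAP's random site-by-treatment effect; variance from the latter adds equally to both models and shrinks the percentages. The public SAP also lacks most text between 4.3.1 (page 11 in its contents list) and Section 5 (page 16), and some inclusion criteria are removed, so further model detail or a restricted baseline range could exist.

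Finally, a late change to a primary model carries a credibility cost. The SAP is already Version 3.0, only assessors are masked, and the sponsor keeps the randomization list. This is a reason to act before unmasking and to give the reason on design grounds.

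**Conclusion.** The point holds as a minor refinement. In the visible text of both documents, one baseline slope serves six visits while the test uses only the last. Whether this matters depends on slope drift and baseline spread, which the documents do not give. Over the assumed range, the 12-month variance is 0.2% to 3.1% higher under mild drift and 1.1% to 9.8% higher under strong drift, against a loss of 0.2% to 0.5% from the added term if the slopes are equal.

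The possible gain is larger than the possible loss, but both are small. The worst tabulated case costs about 2.5 points of power (90.18% to 87.65%) and combines the steepest assumed drift with the widest assumed baseline spread. It does not show that 188 completers or 90% power is wrong on the plan's own inputs. The absence of bias follows from randomization and was seen in simulation with dropout unrelated to MGS; other dropout patterns were not examined.

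**What to change.** In Protocol 12.4.1.2 and SAP 4.3.1, change the fixed-effect list to: treatment, visit, treatment by visit, baseline MGS of the same eye, and baseline MGS by visit. Keep the within-subject eye correlation and the SAP's random site and site-by-treatment effects. Take the 12-month treatment difference and its one-sided 95% lower limit from that model.

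Make the change before unmasking and database lock, and record that it rests on the design and not on accumulated data. If the unpublished SAP text already contains the term, only the two term lists need to be aligned.

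The cost is five extra parameters, about 0.2% to 0.5% in variance if the slopes are in fact equal, and an amendment to both documents. Data collection, margin, time point and sample size do not change.

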12 ANALYSIS PLAN

Continuous variables will be summarized using the number of observations, mean, standard deviation (SD), median, minimum, and maximum, as well as confidence intervals or confidence limits where applicable. Categorical variables will be summarized with counts and percentages from each category. Any deviations to the analysis plan will be updated

Document: TDOC-0056343 Version: 3.0; Most-Recent; Effective; CURRENT

Page 55 of 66

during the course of the study as part of a protocol amendment or will be detailed in the clinical study report.

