12.4.1.2 Analysis Methods

A mixed effects repeated measures model will be utilized to test these hypotheses. The model will include terms for treatment, visit, treatment by visit interaction, and baseline MGS. Within-subject correlation due to eye will also be accounted for in the model. Treatment difference (iLux minus LipiFlow) and the corresponding one-sided 95% lower confidence limit (LCL) will be computed. Noninferiority in change from baseline in MGS will be declared if the LCL is greater than -5.

Alcon - Business Use Only Protocol - Clinical Effective Date: 18-Jun-2019 Version: 3.0; Most-Recent; Effective; CURRENT Document: TDOC-0056343 Page 58 of 66

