12.6 Safety Analyses

The safety endpoints are:

- AEs
- Biomicroscopy findings
- Device deficiencies

There are no safety hypotheses planned in this study. The focus of the safety analysis will be a comprehensive descriptive assessment of occurrence of AEs as well as the other listed parameters.

All AEs occurring from the time a subject signs informed consent to study exit will be accounted for in the reporting. Safety analyses will be conducted using the safety analysis set on a treatment-emergent basis. Descriptive summaries (counts and percentages) for ocular and nonocular AEs will be presented by Medical Dictionary for Regulatory Activities Preferred Terms. AEs leading to study discontinuation, and SAEs will be identified. Individual subject listings will be provided, as necessary.

Individual subject listings will be provided for AEs that occur after signing informed consent but prior to exposure to IP.

Each biomicroscopy parameter will be tabulated by its grade. For select biomicroscopy parameters, counts and percentages of eyes that experience an increase of 1 grade from

Document: TDOC-0056343 Version: 3.0; Most-Recent; Effective; CURRENT

Page 60 of 66

baseline (last assessment prior to study treatment exposure) to any subsequent visit will be presented. A supportive listing will be generated which will include all biomicroscopy data from all visits for those eyes experiencing the increase.

Two listings for device deficiencies, prior to exposure of study treatment and treatmentemergent, will be provided. Additionally, each device deficiency category will be tabulated.

No inferential testing will be done for safety analysis.

[figure not shown]
| 12.9. Cample Circ Inglification |
|---------------------------------|
| 12.8 Sample Size Justification |
| |
| |
| |
| |

Document: TDOC-0056343 Version: 3.0; Most-Recent; Effective; CURRENT

Page 61 of 66

Primary Effectiveness

To demonstrate noninferiority (margin = 5) in change from baseline in MGS as a one-tailed hypothesis with α =0.05, and using a standard deviation of 11.661, 90% power can be attained with a sample size of 188 (94 per treatment group).

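### Does it matter that SAP 4.3.1 adds random site and site-by-treatment effects which Protocol 12.4.1.2 does not list for the primary noninferiority test?

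*SAP*

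**What the plan says.** Protocol 12.4.1.2 specifies a mixed effects repeated measures model with "terms for treatment, visit, treatment by visit interaction, and baseline MGS", and it accounts for the correlation between a subject's two eyes. The decision rule is "Noninferiority in change from baseline in MGS will be declared if the LCL is greater than -5".

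SAP 4.3.1 gives the same terms, the same treatment of the two eyes, the same one-sided 95% limit and the same rule. Between the eye-correlation sentence and the limit it inserts "Site and site by treatment interaction terms will be included as random effects to account for potential effect of sites on treatment difference".

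Three other places bear on the point:

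- The SAP states that it "is based on Version 3.0 of the study protocol". SAP section 10 says of Version 3.0: "The purpose of this revision is to clarify specific reporting considerations and analysis strategies".
- Protocol section 12 says that departures from the analysis plan will be updated "during the course of the study as part of a protocol amendment or will be detailed in the clinical study report".
- SAP section 7 states that, "using a standard deviation of 11.661, 90% power can be attained with a sample size of 188 (94 per treatment group"). Protocol 12.8 gives the same figures.

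**The concern.** There is one primary endpoint and one success rule, so the standard error and degrees of freedom behind that single limit decide the trial. A random site-by-treatment effect adds the site-to-site variation in the treatment difference to the standard error, and it may cut the degrees of freedom towards the number of sites. A random site effect works the other way, by taking between-site variance out of the error. Two documents that differ on these terms could yield two limits from the same data. If nobody had settled which one counts, the choice could be made after seeing the results. The sample size calculation also contains no site component, which raises the question of whether 90% power still holds under the SAP model.

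**Working it through.** **Inputs from the documents.** Margin 5, one-sided alpha 0.05, SD 11.661, 94 per group (Protocol 12.8, SAP 7); approximately 15 sites (Protocol 8).

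**Assumptions.** The readable text gives no site variances and no degrees-of-freedom method. I take a true difference of 0 for power, 15 equal sites, one eye and one visit. Let tau be the SD of site-specific treatment differences (0 to 3 points) and s the between-site SD (0 to 4 points). Total SD is held at 11.661.

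**Step 1: the plan's own figure.** A plain two-sample calculation gives SE = 11.661 × √(2/94) = 1.701. The lower limit lies t(0.95, 186) × 1.701 = 2.81 below the estimate. Power from the noncentral t is 90.04% at 94 per group and 89.76% at 93, so the stated size is reproduced without any site term.

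**Step 2: the limit with site terms.** SE² = 2 × (11.661² − s² − tau²/2)/94 + tau²/15. For tau = 2:

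| s | SE | Margin, 186 df | Margin, 14 df |
|---|---|---|---|
| 0 | 1.766 | 2.92 | 3.11 |
| 4 | 1.666 | 2.75 | 2.94 |

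Without site terms the estimate must exceed −5 + 2.81 = −2.19. With them it must exceed a value between −5 + 2.75 = −2.25 and −5 + 3.11 = −1.89. The two models can therefore disagree only in a narrow band of estimates, and the direction depends on variances that are not given.

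**Step 3: how often the verdict differs.** I used simulation results with 100,000 trials per setting, 15 sites and 6 subjects per arm at each site. The model without site terms is a pooled t test on 178 df. The model with them uses the interaction mean square, pooled with the residual when the interaction variance is estimated at zero, on 14 or 178 df.

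- True difference 0: verdicts differ in 3.1% to 7.5% of trials (14 df) or 2.5% to 4.8% (178 df).
- True difference −5: they differ in 1.0% to 2.4% or 0.9% to 1.6%.
- Most disagreements are a pass without site terms and a fail with them. The reverse reaches at most 1.1%.
- With tau = 0 and s = 0, verdicts at true difference 0 already differ in about 5% (14 df) or just under 3% (178 df). Much of the disagreement therefore comes from the assumed degrees of freedom and the zero-variance rule, not from differences between sites.

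**Step 4: error rate at the margin.** At a true difference of −5, the model with site terms passes 3.5% to 4.1% (14 df) or 4.4% to 5.0% (178 df) for tau 2 to 3. Without site terms and with s = 0, it is 5.6% (tau 2) and 6.5% (tau 3). The SAP model is the one that stays within the nominal 5%.

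**Step 5: power.** Over tau 0 to 3, power runs from 90.0% down to 85.5% (186 df) or 87.5% to 82.5% (14 df) with s = 0. With s = 4 it runs from 93.0% to 88.6%, or 90.8% to 85.8%. The range lies on both sides of 90%, so the stated power is not shown to be wrong.

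**The case for a change.** The strongest case for acting is that the protocol paragraph runs unbroken from the eye-correlation sentence to the limit, so redaction at that spot does not explain the missing terms. A random site-by-treatment effect is also more than a programming detail, because it changes what counts as error in the only limit that matters. No readable text calls the SAP wording an elaboration, and the revision note does not mention it.

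The first two statements stand. What does not stand is the suggestion of an unacknowledged change. The SAP contents list puts Revision History on page 19 and the Appendix on page 22, yet only a few sentences of section 10 can be read. The purpose sentence describes only the step to Version 3.0, and the site terms may have entered in an earlier SAP version. Nor can a missing degrees-of-freedom method be established, since parts of the SAP's analysis text are also not readable. If it is absent, an analyst fitting this model would choose a standard method.

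The power point also has no force as a correction. A two-sample formula is a routine simplification for a trial analysed with a mixed model. It ignores the gains from baseline adjustment and the second eye as well as the cost of site heterogeneity.

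**Conclusion.** No change to the plan. The protocol says what the model will include and does not say that nothing else may enter. The SAP (approved 09 Nov 2020; the protocol took effect 18 Jun 2019) retains all of it, adds the site terms and states a single primary model. An analyst working from the SAP has one model to fit and one limit to compare with −5. That model is usually the stricter of the two and does not inflate the chance of a false noninferiority claim under the settings examined.

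If the sponsor regards the extra terms as a departure from the protocol, Protocol section 12 already lets them be described in the clinical study report. Repeating the sentence in the protocol would alter no analysis, figure or conclusion.

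The size of the effect, a few percent of trials with a different verdict, rests on assumed site variances, equal sites and a one-eye, one-visit stand-in for the full repeated measures model. It indicates scale only. The conclusion does not depend on it, because the SAP already fixes which model is used.
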